6.1.2.2 Guidelines for Dose De-escalation

While it is not expected that there will be a need for dose de-escalation in this trial, if there is evidence of drug accumulation based on rising peak and trough levels of MarzAA or other laboratory parameters, then the subject's dose level will be reviewed by the PI and Sponsor, or designee, and a determination to hold treatment at the current dose level or decrease to the lower dose level will be made. This determination will be made in conjunction with the independent Medical Consultant for Safety Oversight.

6.1.2.3 Guidelines for Treatment Interruption

Daily SC study injections will be interrupted, as needed, when:

- A surgical procedure is needed
- There is a medical event requiring extended (>48 hours) hospitalization
- If there is a thrombotic event
- If there is clinical evidence of inhibitor formation
- If there are laboratory results suggesting an antibody may be developing

Daily SC study injections may be interrupted, as needed, when:

- A spontaneous bleeding event occurs
- A traumatic bleeding event occurs

Subjects will use their current treatment regimen for any spontaneous or traumatic bleed that occurs while on study. If treatment for a spontaneous or traumatic bleeding episode is needed, then subjects will contact the clinical investigative team immediately to report the event; treatment dose administered; and determine follow-up plans for that event, including to arrange for a blood specimen to be drawn (if feasible) before further administration of either study drug or bypassing agent used for treatment. This information will also be recorded in the subjects' diary.

6.2 PREPARATION/HANDLING/STORAGE/ACCOUNTABILITY

6.2.1 Acquisition and Accountability

Upon receipt of the MarzAA shipment, the pharmacist, or a designee, will conduct an inventory and return an acknowledgement that all IP was received frozen and undamaged, thereby maintaining the Good Manufacturing Practice (GMP) status of the product during shipment.

MAA-201 VERSION 2.0

All used and unused investigational product must be returned by the subject to the study site. Subjects must return all investigational product packages and vials (including used, empty, and unused vials) for reconciliation of IP.

The investigator, or approved representative (eg, pharmacist) must maintain adequate records documenting the receipt, use, loss, or other disposition of the investigational product. The sponsor will supply drug accountability forms to be used in this study.

The sponsor or designee will arrange for the return of unused investigational product. The IP destruction procedure for used vials is to be decided locally to comply with local regulations and procedures.

Drug accountability will be reviewed by the monitor during routine monitoring visits. No IP can be destroyed or returned until the study monitor has reconciled all vials of IP.

6.2.2 Product Storage and Stability

The investigator, or an approved representative, eg, pharmacist, will ensure that all investigational products are stored in a secured area with controlled access under recommended storage conditions and in accordance with applicable regulatory requirements. The IP and its storage and preparation requirements will be provided by the Sponsor, or designee.

Investigational product should be stored in its original container and in accordance with the drug label. The Sponsor will provide the Investigator with packaged IP in accordance with specific country label requirements.

Site systems must be capable of measuring and documenting (for example, via a log), at a minimum, daily minimum and maximum temperatures for all site storage locations (as applicable, including frozen, refrigerated and/or room temperature products). This should be captured from the time of investigational product receipt throughout study. Even for continuous monitoring systems, a log or site procedure which ensures active daily evaluation for excursions should be available. The operation of the temperature monitoring device and storage unit (for example, refrigerator), as applicable, should be regularly inspected to ensure it is maintained in working order.

Any excursions from the product storage conditions should be reported upon discovery. The site should actively pursue options for returning the product to appropriate storage conditions, as soon as possible. Deviations from the storage requirements, including any actions taken, must be documented and reported to the Sponsor, or designee.

Once an excursion is identified, the investigational product must be quarantined and not used until the Sponsor, or designee, provides documentation of

MAA-201 VERSION 2.0

permission to use the investigational product. Specific details regarding information the site should report for each excursion will be provided to the site.

Receipt of materials, door opening and closing, and other routine handling operations where the product(s) are briefly out of labeled temperature range are not considered excursions. Site staff will instruct subjects on the storage requirements for take home medications including how to report temperature excursions.

6.2.3 Preparation

MarzAA will be provided as a powder for injection, at a 4.62 mg/vial dosage strength, and is supplied in a 5-mL vial. The lyophilized drug product will be reconstituted for IV and SC injection.

Details regarding the dosing administration, both at the study site and in the homecare setting, will be provided by the Sponsor, or designee.

At the study site, both the MarzAA IV dose and SC dose will be prepared and administered by an appropriately qualified and experienced member of the study staff (eg, physician, nurse, physician assistant, nurse practitioner, or pharmacist) as allowed by local, state, and institutional guidance.

In the homecare setting, the MarzAA SC dose will be prepared and administered by the study subject or subject caregiver/guardian.

6.3 MEASURES TO MINIMIZE BIAS: RANDOMIZATION AND BLINDING

The study is an open-label study; subjects and members of the clinical study team will not be blinded to treatment.

6.4 STUDY INTERVENTION COMPLIANCE

Reasonable efforts should be made to ensure that study drug administration is administered daily in the morning. However, if an unavoidable disruption of the daily administration occurs and a dose is not administered then the subject should be instructed to continue beginning the following day in the morning.

If the subject misses two or more daily doses, then a spontaneous bleeding event will result in a dose escalation only if it occurs 4 days or longer after resumption of the daily administration.

MAA-201 VERSION 2.0

6.5 CONCOMITANT THERAPY

Enrolled subjects will record all concomitant medications administered from the Screening Visit to Study termination (including the date and time of administration) in their diary.

For this protocol, a prescription medication is defined as a medication that can be prescribed only by a properly authorized/licensed clinician. Medications to be reported in the electronic Case Report Form (eCRF) are concomitant prescription medications, over-the-counter (OTC) medications and supplements.]

There are no concomitant medication restrictions. However, individuals are excluded if they have been on a prophylactic treatment regimen with a FVIII or FIX replacement factor or a bypassing agent prior to enrollment.

If an individual has previously been enrolled on a clinical trial evaluating a treatment for prophylaxis other than a modified rFVIIa (as specified in exclusion criteria #2) or Emicizumab (ACE910)⁴⁹, Fitusiran (ALN-AT3SC)^{50,51}, or one of the anti-TFPI agents (Concizumab [mAb2021]⁵², BAY1093884⁵³, PF-06741086⁵⁴) in clinical investigation he will be permitted to enroll onto this study, provided it is greater than 30 days since exposure to that study drug.

The following medications will be permitted during the study:

- In the event of spontaneous or traumatic bleeding, treatment for a spontaneous or traumatic bleeding episode will be permitted using the subject's current treatment regimen which could be FEIBA[®], NovoSeven[®], or a high dose regimen utilizing a FVIII or FIX product.

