Study Treatment and Assessments:

Part 1a: Single IV administration

Each subject will receive an IV dose of 18 µg/kg MarZAA. PK, PD, and safety assessments will be collected pre-dose and post-dose at 5 and 30 minutes and at Hour 1, 3, 6, 9, 12, and 24.

Part 1b: Single SC administration

After the initial 24 hours, the same subject will receive a SC dose of 30 µg/kg MarZAA. PK, PD, and safety assessments will be done at pre-dose and repeated at Hour 3, 5, 7, 9, 12, 24, 30, and 48. At any time during this period, subjects will be trained by appropriate study staff to self-administer a SC injection.

Part 2: Daily SC administration

At Day 1 of daily SC dosing, subjects will begin their self-administered dosing regimen. MarZAA will be self-administered by subjects daily (at approximately the same time every day), starting with a SC dose of 30 µg/kg MarZAA. At each dose, subjects will record the day and time of the SC injections in their diary. If a spontaneous bleeding episode (defined as one that is precipitated by normal activities of daily living [ADL]) occurs before the fifth daily dose, subjects will continue at the current dosing level. If a spontaneous bleeding episode occurs after the fifth daily dose, the MarZAA dose will be escalated to the next dose level. Three dose escalations are allowed during part 2: 60, 90, and 120 µg/kg (maximum dose). At each dose level escalation, safety and PK/PD will be monitored to ensure that dose escalation to a higher dose level is appropriate. If a subject requires a third dose escalation to the fourth dose level, then they will continue treatment with that dose for 50 days and complete the study, regardless if a spontaneous bleeding episode occurs during the highest treatment dose level.

Treatment of a spontaneous bleeding episode: Subjects will use their current bypass regimen for any spontaneous or traumatic bleed that occurs while on study drug. If treatment for a breakthrough bleeding episode is needed, then subjects will contact the clinical investigative team immediately to report the event; treatment dose administered; and determine follow-up plans for that event, including to arrange for a blood specimen to be drawn (if feasible) before further administration of either study drug or bypassing agent used for treatment. This information will also be recorded in the subjects' diary.

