5.2 EXCLUSION CRITERIA

An individual who meets any of the following criteria will be excluded from participation in this study:

1. Receiving prophylaxis treatment.
2. Previous participation in a trial involving Subcutaneous Administration of rFVIIa (Novo Seven or MOD-5014) or any trial using a modified rFVIIa such as: NN1731 or BAY86-6150. Prior participation in a trial of LR769 or rFVIIa-FP (CSL689) is permissible.
3. Previous participation in and subsequent treatment in a clinical trial within the previous 30 days or 3-half-lives or absence of clinical effect, whichever is longer.
4. Known positive antibody to FVII or FVIIa detected by central laboratory at screening.
5. History of clinically relevant coagulation disorders other than congenital hemophilia A or B.
6. Platelet count $< 100,000$ based on screening laboratory assessments.
7. Advanced atherosclerotic disease (i.e. known history of CAD, ischemic stroke, etc.), or known DVT or considered to be at a high risk of VTE as judged by the Investigator.
8. Known or suspected allergy to trial product or related products.
9. Absolute CD4 count < 200 cells/ μL .

MAA-201 VERSION 2.0

10. Receiving IMT.
11. Compromised hepatic or renal function:
 - a. ALT and AST levels ≥ 5 times ULN
 - b. TBIL level ≥ 2 mg/dL (>35 $\mu\text{mol/L}$) unless there is a known history of GS
 - c. Serum albumin \leq LLN
 - d. Serum Cr level >1.25 x ULN
12. Inability or medical, psychosocial, or familial issues that might prevent full participation and cooperation with the procedures and requirements of the clinical trial as determined by the potential subject and physician investigator.

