### 5.6 PHARMACOKINETIC (PK) POPULATION

PK population is defined as any patient who has received one dose and has at least one measured PK concentration post-dose. The PK data will be listed for this population and used in all PK analyses. The PK data for subjects with protocol deviations affecting the results may be excluded from summaries and analyses. Any Protocol deviations pertaining to the validity of PK analyses (and thus inclusion in the PK population) will be determined before the database lock (and receipt of PK data), based on a review of all protocol deviations.

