**Version 2.0**

**Syneos Health #1009647**

results may be excluded from summaries and analyses. This will be determined before the database lock based on review of all protocol deviations.

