## 6. GENERAL ASPECTS FOR STATISTICAL ANALYSIS

### 6.1 KEY DEFINITIONS

#### 6.1.1 Baseline

Baseline is defined as the last assessment (pre-dose) prior to the first administration of the study drug in Part 1a. This baseline will be used for both part 1a and part 1b, and will be used in all efficacy and safety analyses in [section 12](#)

For the baselines for PK and PD analyses, they will be defined separately in [Section 9](#) and [Section 10](#).

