### 9.1 PK SAMPLING SCHEDULE

PK sampling schedule will be specific to each part and dose administration. The PK data will be measured as MarzAA antigen concentration and activity levels. Additional PK data will include FVII, FVIIa activity.

Part 1a - single IV dose of 18 µg/kg MarzAA. PK sampling - predose, and post-dose at 5 and 30 minutes and Hour 1, 3, 6, 9, 12, and 24.

Part 1 b - single SC dose of 30 µg/kg MarzAA. PK sampling - pre-dose and Hour 3, 5, 7, 9, 12, 24, 30, and 48 post-dose.

Part 2 - daily SC dosing with variable dose to be determined.

PK sampling - Day 1 (Pre-dose and Post-dose Hour 7), Day 3 (Pre-dose), Day 5 (Pre-dose), Day 7 (Pre-dose). In the absence of spontaneous bleeding for the first dose level in Part 2 of the study, trough antigen and activity will be measured on days 14, 21, 28, and 50.

In case of spontaneous bleeding the PK samples will be taken within 6 hours of the spontaneous bleed and a pre- and 7 hours post-dose on Day 7, 14, 21, 28, and 50 after dose escalation.

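### On-demand rescue is allowed before and during Part 1 but is not a protocol deviation, so the SAP leaves post-rescue samples in the PD baselines and in the FVII/FVIIa activity and PD summaries

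*Protocol*

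**What the plan says.** **Use of haemostatic agents.** Protocol 6.5 says "There are no concomitant medication restrictions". Its next sentence sets one limit at entry: "individuals are excluded if they have been on a prophylactic treatment regimen with a FVIII or FIX replacement factor or a bypassing agent prior to" enrolment. It then lists treatment of a bleed with FEIBA, NovoSeven or high-dose FVIII/FIX as permitted. The Synopsis adds "Subjects will use their current bypass regimen for any spontaneous or traumatic bleed that occurs while on study drug", and Protocol 4.1 repeats this; neither makes an exception for Part 1. The washouts concern trial drugs only: exclusion criterion 3 ("Previous participation in and subsequent treatment in a clinical trial within the previous 30 days or 3-half-lives", or longer) and a 30-day rule in 6.5. The Part 1a pre-dose list (8.2.2.1) reviews concomitant medication and haemophilia history but sets no condition on recent on-demand treatment.

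**Exclusion of data.** SAP 5.6: "The PK data for subjects with protocol deviations affecting the results may be excluded from summaries and analyses". SAP 5.7 gives the same ground for PD data and adds "This will be determined before the database lock based on review of all protocol deviations". SAP 9.3.2 and 10.3.2 repeat it. Other filters cover samples outside the time windows (9.3.1, 10.3.1) and PK parameters with an unreliable terminal slope or more than 25% AUC extrapolation (9.2).

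**Baselines.** SAP 6.1.1: "Baseline is defined as the last assessment (pre-dose) prior to the first administration of the study drug in Part 1a". The same section defers the PK and PD baselines to Sections 9 and 10. SAP 10.3.2 takes the last PD value before the first dose, separately for Parts 1a, 1b and 2. SAP 10.4 uses the value before the first dose at the first dose level.

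**Analytes.** SAP 9.1: "Additional PK data will include FVII, FVIIa activity". PT, aPTT, fibrinogen, TGT, D-dimer, F1+2 and TAT are PD (10.1).

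**The concern.** Every subject treats bleeds on demand and enters with at least 12 bleeds a year. Protocol 2.2 describes bypassing agents as driving the conversion of prothrombin to thrombin, and wt-rFVIIa is itself FVIIa. FVIIa activity, the coagulation assays and the thrombogenicity markers therefore respond to rescue as well as to MarzAA.

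The direction depends on timing. Rescue shortly before a part's pre-dose sample raises that baseline and can hide a MarzAA-related rise. Rescue after dosing adds to the apparent MarzAA response. Part 1b follows Part 1a directly, so rescue during Part 1a can affect both the end of the IV profile and the Part 1b baseline.

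At stake are the secondary objective of comparing thrombogenicity markers after SC 30 µg/kg and IV 18 µg/kg, and the secondary endpoint of change in coagulation parameters from pre-dose. Both rest on 12 subjects. Without a rule, the team must either average an affected profile in or remove it by judgement late in an open-label study.

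**Working it through.** The plan gives no figure for rescue use in Part 1, so there is none to reproduce.

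**Step 1: does any stated filter remove a post-rescue sample?**

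| Filter | Trigger | Reaches permitted rescue? |
|---|---|---|
| SAP 5.6, 5.7, 9.3.2, 10.3.2 | Protocol deviation affecting results | No: treating a bleed is allowed |
| SAP 5.8, concomitant-medication category | Must first be a deviation | No |
| SAP 9.3.1, 10.3.1 | Sample outside its time window | No |
| SAP 9.2 | Poor terminal slope, or extrapolation above 25% | Not aimed at it; does not cover PD |
| SAP 7.6 | Hemophilia medication tabulated | No link to PK/PD samples |

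SAP 9.3.1 and 10.3.1 set pre-dose values below quantification to zero, but no rule covers a quantifiable pre-dose value.

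**Step 2: where the samples end up.** They enter the per-part PD baselines (10.3.2), the Part 2 comparison baseline (10.4), the coagulation change from baseline (8.2.3, using the 6.1.1 baseline), and the Part 1 FVII/FVIIa activity and PD summaries (9.3.3, 10.3.3).

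**Step 3: how often.** Inputs: ABR 12 (inclusion criterion 2), 12 subjects, and Part 1 of 24 + 48 = 72 h = 3 days. Assumptions: Poisson bleeding, no MarzAA effect yet, and ABR 24 as an upper case.

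- Per subject: p = 1 − exp(−ABR × days / 365.25)
- At least one of 12: 1 − (1 − p)^12

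| ABR | Period | p | Expected of 12 | At least one |
|---|---|---|---|---|
| 12 | Part 1, 3 days | 1 − exp(−0.0986) = 9.4% | 1.13 | 69% |
| 24 | Part 1, 3 days | 1 − exp(−0.1971) = 17.9% | 2.15 | 91% |
| 12 | 24 h before dosing | 1 − exp(−0.0329) = 3.2% | 0.39 | 33% |

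A bleed late in Part 1 touches little. After the 30 h SC sample only the 48 h sample remains. Counting only bleeds before that point (24 + 30 = 54 h = 2.25 days) gives, at ABR 12, 1 − exp(−12 × 2.25 / 365.25) = 7.1%, or 0.86 of 12, with a 59% chance of at least one. At ABR 24 it is 13.7%, 1.65 of 12 and 83%.

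**Step 4: carry-over into the pre-dose sample.** With the wt-rFVIIa half-life of 2.3 h in Protocol 2.2, the fraction left is 2^(−t/2.3): 16% at 6 h, 2.7% at 12 h and 0.07% at 24 h. Concentration carry-over of wt-rFVIIa therefore matters mainly within about 12 h of dosing. The documents give no corresponding figure for FEIBA or for recovery of the PD markers.

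**The case against.** The strongest reply is that Part 1 PK/PD is descriptive in a small Phase 2 study and the data needed to spot a problem already exist. Medication dates and times are recorded from screening, haemostatic drugs are timed, individual profiles are plotted, and medians and ranges are reported. That stands as far as it goes: an affected profile would probably be visible. But no rule says what to do with it.

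Four stronger readings are tempting, and the documents do not support them.

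- A reader might infer that haemostatic agents are wholly unrestricted. They are not: prior prophylaxis is excluded, and only on-demand use is open.
- A reader might infer from SAP 6.1.1 that one contaminated Part 1a sample is the baseline for every marker throughout. It governs the SAP 8.2.3 coagulation summary, which contains no thrombogenicity markers. PD baselines are set per part.
- A reader might infer that bioavailability, clearance and volume are compromised. SAP 9.2 derives these for MarzAA only, and whether its antigen and activity assays read the rescue products is not stated. If they did, inflating one subject's SC AUC by 50% would multiply that subject's F by 1.50, and the same inflation of the IV AUC would multiply it by 1/1.5 = 0.67. That remains conditional.
- A reader might add 1 to 3 days of persistence before dosing and reach a 79–99% chance of at least one affected subject. That assumes every bleed is treated and a persistence that the documents do not give.

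It is also fair that dropping points from a 24 h or 48 h profile can itself distort an AUC. The fix has to allow for this.

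**Conclusion.** The gap is real. Following the stated rules keeps samples taken after permitted rescue in the FVII/FVIIa activity and PD baselines and summaries, and presents them as MarzAA effect. At the minimum entry rate about 1.1 of 12 subjects would bleed during Part 1, with a 69% chance of at least one; at an assumed ABR of 24 the chance is 91%. These figures rest on Poisson bleeding and no MarzAA effect yet. They are upper bounds for rescue use, since some bleeds go untreated, and a late bleed affects few samples. The Part 1 figures need no assumption about carry-over before dosing. How far an affected profile shifts a mean cannot be computed from the documents.

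**What to change.** Before database lock, amend SAP 5.6, 5.7, 9.3 and 10.3 as follows.

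1. Pre-specify an interval for each agent and analyte, set by the sponsor. Using recorded medication times, flag every FVII/FVIIa activity and PD sample taken within that interval after a bypassing, FVIII or FIX product, whether or not a deviation occurred. Include MarzAA activity if its assay cross-reacts.
2. Leave flagged samples out of baselines and by-time summaries.
3. Flag any AUC, AUE, Cmax or Emax derived from an affected profile and exclude it from the summary, rather than interpolating across dropped points.
4. If a part's pre-dose PD sample is flagged, use the last unflagged sample before the first MarzAA dose as baseline. Screening already includes coagulation and thrombogenicity markers (Protocol 8.2.1).
5. Keep all values in listings and give an all-data sensitivity summary.

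The clinical team should reconcile the two statements in Protocol 6.5: no restrictions, followed by a list of what is permitted.

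The cost is SAP wording and programming from times already collected. The downside is that one or two of 12 profiles may leave the main Part 1 summary; the sensitivity summary shows what that changes.

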7. STUDY INTERVENTION DISCONTINUATION AND PARTICIPANT DISCONTINUATION/WITHDRAWAL

7.1 DISCONTINUATION OF STUDY INTERVENTION

Discontinuation from study intervention does not mean discontinuation from the study, and remaining study procedures should be completed as indicated by the study protocol.

Any new clinically relevant finding will be reported as an AE.

